## 2. Study Design and Statistical Procedures

Our study will consist of a small-scale RCT of RtG in New York City (RtG also has a Boston site that will not be currently part of the study). Late-term pregnant mothers are typically referred to RtG from outside service providers, most of which are hospital staff across New York City and a few non-profits. From these referral forms, select directory information is entered into a Google document that is shared with Drs. [name], [name], and their staff: client's first and last name, due date, referral date, phone number and email, age bracket of over or under 18, and referral agency. No other information, including any health-related information, is passed on to Columbia staff. Columbia staff then initiate contact with referred clients—after a client agrees to study participation and schedules their baseline survey appointment they are randomized by Columbia staff to either the treatment or control group. If a client refuses study participation the client is not randomized by Columbia staff and the referral is passed back to Room to Grow, where the referral is randomly assigned to either be in our out of the program; this process ensures that all referrals undergo randomization regardless of their decision to participate in the study. The treatment group will consist of mothers that were randomly selected to receive Room to Grow services, which include three years of social and practical support for the mother and baby. Mothers in the control group will not receive Room to Grow services. Room to Grow receives more referrals than they can accommodate at any given time, so the randomization process is a fair and equitable system for assigning mothers program slots. As stated above, a participant's decision to partake in the Columbia Study will not affect their chance of receiving Room to Grow services—mothers who refuse to participate in the study are passed back to Room to Grow, where they are randomly assigned in or out of the program. Room to Grow uses a pre-generated list of slot assignments of either “in” or “out”—when a referral is passed back its consecutive position on the list indicates if the referral is accepted into the program.

Additional funding has allowed for the expansion of recruitment size; we have recruited and enrolled 160 treatment group subjects and 160 control group subjects. Treatment and control group subjects will both be given an incentive of \$50.00 in cash for their participation in the 45 minute survey, and control group subjects will also be given a gift tote filled with approximately \$75.00-\$100 worth of developmentally-appropriate gifts for their impending child (this being the only difference between the treatment and control group consent forms attached to the protocol – the different versions of the consent forms only differ in their description of the compensation offered). Study participants who are selected in the RtG lottery will receive a follow-up call from RtG informing them of their selection, and Columbia staff will call the participants who do not receive a place in the lottery and invite them to remain part of the study approximately four business days after completing the baseline survey.

Experienced interviewers will conduct the interviews in either English or Spanish. Subjects will be enrolled in the “Columbia Mothers and Babies Study” and follow-up permission and information will be collected at that point (i.e., subjects will be asked for best modes of future contact and have the opportunity to provide friends’ and family members’ contacts, email addresses, etc.). Approximately 4 months after the completed baseline interview, subject will be mailed a jotter and a letter with Columbia’s contact information so that participants can reach out with updated contact information. Approximately 9-10 months after the baby is born, participants who agreed will be followed up with on the phone and will be asked to participate in a 40 minute survey with a \$35 incentive. Due to the transient nature of this study sample, we anticipate that it will be more difficult to reach some subjects than others. For subjects that do not refuse, but who have not completed the follow-up survey after 10 attempts, we will be offer an additional \$15 incentive, bringing the total compensation to \$50.

Subjects enrolled in the study who consented to future follow-up will again be contacted when their babies are 25 months and invited participate in a 45 minute phone survey with a \$40 incentive. In line with procedures from the 10 month follow-up, subjects that do not refuse, but who have not completed the follow-up survey after 10 attempts, will be offered an additional \$15 incentive, bringing the total compensation to \$55.

\*Added 12/2/2020\*

Subjects enrolled in the study who consented to future follow-up at 25M, will again be contacted when their babies are 42 months old. They will be invited to participate in a 55-minute phone survey with a \$40 incentive. In line with procedures from the 10-month follow-up and 25 month follow-up, subjects that do not refuse, but who have not completed the follow-up survey after 10 attempts, will be offered an additional \$15 incentive, bringing the total phone survey compensation to \$55 for these subjects.

Due to the transient nature of this population, we anticipate that a small percentage of subjects will no longer be living with their babies at the 9-10 month or 25-month follow-up. We will make an effort to keep these subjects in the study, as they offer valuable insight into a subset of the population. Subjects will be invited to participate using the same protocol, and the same approved 10M or 25M survey. All subjects will be asked if they are living with their babies. If a subject indicates that they are not living with their baby, the survey version they are administered will omit sections pertaining to child and family routines. Subjects will still be surveyed on sections pertaining to maternal health, hardship and employment. Subjects will still receive full compensation for their participation.

At the time of the 25M follow-up survey, if a subject indicates they are no longer living with their child, we will still invite the subject to complete a slightly shortened version of the 25M survey omitting sections about child and family routines. In addition, we will also ask the subject to voluntarily provide contact information for the new primary caregiver of the child. If contact information is provided, we will attempt to contact the new primary caregiver and invite them to participate in the 25-month PCG follow-up survey. The PCG follow-up survey is similar to the previously approved 25M survey, with an added demographics section from the previously approved Baseline survey. All subjects who complete versions of the 25M follow-up survey will receive an incentive of \$40.

\*Added 4/14/2021\*

We will follow the same 25M follow-up survey procedures if a subject indicates they are no longer living with their child. If primary caregiver information is unavailable we will ask the subject to voluntarily provide contact information for the primary caregiver to invite them to participate in the 42-month PCG follow-up survey. The PCG follow-up survey is similar to the previously approved 42M survey, with an added demographics section from the previously approved 25month PCG follow-up survey. All subjects who complete versions of the 42M follow-up survey will receive an incentive of \$40.

We plan to conduct an in-person baseline assessment (see attached survey instrument) late in the third trimester of pregnancy (weeks 28-34), and conduct phone survey follow-ups at 9-10 months (10M) and 25 months (25M). Our measures fall within five main categories: 1) Demographics; 2) Financial security; 3) Maternal mental health and stress; 4) Parenting quality and, 5) Child Outcomes.

To ensure that all subjects have some access to mental health support, all subjects in the control group receive a flyer with mental health resources in all five boroughs; treatment group subjects receive mental health resources from RtG.

In addition to the survey work described above, our project will include a process evaluation of RtG. This process evaluation will be funded by RtG's evaluation budget, but we believe that it is complementary to the RCT project described here. It is important to understand how RtG delivers services in order to assess program fidelity and dosage. Process data collected during the intervention from treatment families includes timing and duration of visits, the number and nature of touch-points in between routine visits, referrals and accessibility to means-tested benefit programs and community resources, and the scope and achievement rates for short- and long-term goals. This information will document the precise type and amount of service constituted by the intervention, which will be key for future replication or adaptation of the RtG model.

We will be collecting survey data using the Qualtrics service. This service is widely used in the social sciences, and maintains strict security and privacy standards.

Their security statement is available here: <https://www.qualtrics.com/security-statement>

And their privacy statement here: <https://www.qualtrics.com/privacy-statement>

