## Background

### Study Purpose and Rationale:

**Study Purpose:** Our research project is to launch a small-scale randomized controlled trial (RCT) of an innovative program in New York City called Room to Grow (RtG). RtG's mission is to enrich the lives of babies born into poverty throughout their critical first three years of development. The research-informed program model combines tailored, one-on-one sessions with an expert clinical social worker in-person every three months plus ongoing communication (phone and email), provision of essential baby items including books, toys, clothing, and equipment (retail value of in-kind items over three years averages \$10,000), and connections to vital community resources (e.g., housing, entitlements, child care, social services). The goal of RtG's innovative program is to help parents increase the probability that their children will enter school ready to learn and continue on to meet their full potential in education, work, and citizenship. The therapeutic, psychodynamic approach and robust three-year long relationship with families is designed to act as the catalyst for sustainable, long-term change in parenting methods and family system stability. Critically, and in contrast to other programs aimed at improving parenting and child development, RtG believes that providing concrete material assistance enhances the effectiveness of counseling and referrals to low-income families by reducing economic stress and freeing up scarce resources. The program builds on decades of research on the importance of parenting supports for low-income families and their children, the significance of concrete material support and poverty reduction in enhancing children's health and development, and the recognition that the early years are an effective time to provide critical supports that influence long-term outcomes. Numerous programs, such as home-visiting models that provide parenting supports to low-income new mothers have shown promising results (Cates et al., 2016; Peacock et al., 2013). After decades of correlational research establishing relationships between income, poverty, and children's health and development, there is an emerging literature providing convincing causal evidence that income matters for child outcomes (Duncan, Morris, and Rodgrigues, 2011; Chaudry and [name], 2016). Both strains of this research build upon additional research that clearly suggests early childhood is a key period of vulnerability where interventions can make a lasting difference in the fortunes of low-income children and their families (Duncan, Magnuson, Kalil, and Ziol-Guest, 2012). Our research will build upon this literature, by testing an intervention that combines *both* parenting supports and meaningful provision of material support - in essence, assessing whether a combined approach can prove potentially more powerful than the sum of its parts. **Research Questions:** Given the topic outlined above, our research will provide answers to a number of important research questions. 1) Does random assignment to RtG alleviate parents' experiences of material hardship and financial stress? 2) Does random assignment to RtG enhance the quality of parents' home environment and interactions with children? 3) Does random assignment to RtG enhance parents' connection to essential community and health services? It should be noted that our project is designed to investigate proximal outcomes. Over the long-term, our team hopes to build upon these proximal outcomes and to eventually follow children through school-age, as well as greatly expand the number of children that are included in the RCT project.

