**Data:** Our project will rely almost entirely on primary, proximal data. As noted above, after randomization, both treatment and control group subjects will engage in an in-home interview with experienced Columbia staff. These surveys will be approximately 45 minutes in length and subjects are paid \$50.00 for their time. Critically, expected baby due dates will be collected for both groups, in order to plan for timing of subsequent follow-up(s). Subjects will be contacted following the birth of their child with general congratulations and a few months later via mail or other methods to inquire if any changes have occurred to their contact information and to remind them that Columbia staff will be calling them when their baby is around ten months old to schedule a follow-up survey. 10.5, 25, and 42-month follow-up surveys will be conducted via phone (and potentially online for some subjects) by the Columbia Population Research Center's experienced survey research team. The in-person visit will include a brief assessment of the receptive vocabulary (ROWPVT-4) of the child, an assessment of the child's executive function skills, a follow-up survey, and assessments of parenting. In addition, we will request the parent's consent for administrative record linkage to information from the NYC Department of Education (e.g. test scores, grade level). The three types of data collected - repeated survey data, administrative records, and in-person visit based assessments - will be combined into a single dataset for analysis.

---

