## Statistical Procedures:

**Measures:** We plan to conduct a baseline assessment late in the third trimester of pregnancy (weeks 28-34) as an in-person home visit and a follow up survey over the phone when the baby is ten months, twenty-five, and forty-two months old. Our measures fall within five main categories: 1) Demographics; 2) Financial security; 3) Maternal mental health and stress; 4) Parenting quality, and 5) Child Outcomes.

**1) Demographics:** We will measure a standard set of demographic variables at baseline, including age, a full household roster (age, gender, and relationship to respondent for all members of the household), education, employment, race/ethnicity, immigration status, and a global measure of total household income.

**2) Financial security:** We will collect detailed measures of financial stress and material hardship. Financial stress measures will be adapted from the Fragile Families and Child Wellbeing Study, while material hardship measures will be adapted from the Survey of Income and Program Participation, the Fragile Families study, and the Robin Hood Poverty Tracker. Hardship measures will include indicators of food insecurity, housing hardship, utility hardship, medical hardship, and general financial hardship (e.g., running out of money between pay cycles). We also plan to develop new measures of frequency and intensity of hardships in order to capture gradations beyond simple yes/no measures that are standard in the literature.

**3) Maternal mental health and stress:** We will measure maternal depression and stress both at baseline and follow-up with identical measures.

The Parenting Stress Index Short Form (PSI) was developed based on the theory that total parental stress is a function of child and parent characteristics, as well as situational variables. The short form contains 36 items in three main domains: parental distress, parent-child dysfunctional interaction, and difficult child. The total parenting stress score describes the overall level of parenting stress that an individual is experiencing. Internal consistency (Cronbach's alpha) for the PSI (Short-Form) ranges from 0.80-0.91 and test-retest reliabilities from 0.68-0.85. In the 10 month survey we will only include the attachment subscale.

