#### **Inhibitory Motor Control (EF-Touch: Pigs game)**

This task measures inhibitory motor control and is a standard go no-go task (Durstun, Thomas, Yang, Ulug, Zimmerman, & Casey, 2002). Children are presented with a large green button on the screen that makes a "popping" sound when it is touched. Children are instructed to touch the button every time that they see an animal (the 'go' response) except when that animal is a pig (the 'no-go' response). No-go responses vary in difficulty depending on how many go responses preceded them. In the pretest phase, children are asked to identify all of the animals. During administration items, the task is presented in varying numbers of go trials prior to each no-go trial, including, in standard order, 1-go, 3-go, 3-go, 5-go, 1-go, 5-go, 7-go and 7-go. There are 40 items. The score on this activity is a proportion from 0 to 1, zero indicating no items correct and 1 indicating all items were correct.

Statistical procedures will include comparisons of outcomes between the treatment and control groups. Given the small nature of the sample, and concomitantly limited statistical power that entails, our analyses will focus on understanding patterns of associations across outcomes rather than a strict focus on statistical significance. That said, formal tests of significant differences will still be performed.

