**Research Question(s)/Hypothesis(es):**

1) Does random assignment to RtG alleviate parents' experiences of material hardship and financial stress? 2) Does random assignment to RtG enhance the quality of parents' home environment and interactions with children? 3) Does random assignment to RtG enhance parents' connection to essential community and health services?

---

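### The questions are about random assignment, but the plan names no analysis set or missing-data method for a follow-up in which it expects uneven response

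*Combined protocol and SAP*

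**What the plan says.** Each of the three research questions is framed on assignment; the first reads "Does random assignment to RtG alleviate parents' experiences of material hardship and financial stress". The quantitative analysis is given in the closing paragraph of Statistical Procedures, after the description of the Pigs game: "Statistical procedures will include comparisons of outcomes between the treatment and control groups". That paragraph adds that formal tests will be done and that patterns across outcomes will matter more than strict significance.

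Follow-up outcomes come from surveys by phone, possibly online for some, at about 10, 25 and 42 months (Study Design). At 10 months, "participants who agreed will be followed up with on the phone". On response, section 2 (Study Design and Statistical Procedures) says: "Due to the transient nature of this study sample, we anticipate that it will be more difficult to reach some subjects than others".

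The measures taken concern conduct:
- contact details of friends and family;
- a mailed reminder;
- a further $15 for mothers who have not refused but have not completed after 10 attempts;
- continued surveys on hardship and maternal health for mothers no longer living with the child.

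No section names an analysis set, an expected response rate, a report of response by arm, weighting, imputation or a sensitivity analysis.

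**The concern.** A mother who is not surveyed at a wave has no outcome for that wave. A bare comparison of the arms then estimates a difference among responders, while the question concerns everyone assigned. The two can differ if response differs by arm, or if non-responders differ from responders by a different amount in each arm.

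Both are plausible here. Treatment mothers have in-person sessions every three months plus contact in between; controls have no programme contact. Transience may also go with the outcomes: "Hardship measures will include indicators of food insecurity, housing hardship, utility hardship, medical hardship, and general financial hardship". If the least settled controls drop out more often, the remaining controls look better off and a true benefit is understated. If the pattern is reversed, it is overstated. Because the plan relies on patterns across outcomes, a shift common to several hardship and stress measures could be read as a consistent finding.

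**Working it through.** The plan gives no response rate, effect size, SD, alpha or power, so there is no figure of its own to reproduce. From the documents: "we have recruited and enrolled 160 treatment group subjects and 160 control group subjects", so n = 160 per arm. Everything else below is an assumption.

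**Bias formula.** Score outcomes so that higher is worse. Let r be the response rate in an arm and d the amount, in SD, by which its non-responders are worse off than its responders.
- Full-arm mean = responder mean + (1 − r) × d.
- Bias of the responder contrast (treatment minus control) = (1 − rC) × dC − (1 − rT) × dT.
- With the same d in both arms, this is (rT − rC) × d.

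A positive value makes treatment look worse. It moves a true benefit larger than the bias towards the null.

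| Response, treatment / control | Bias, d = 0.2 to 0.5 | Share of an assumed 0.25 SD effect |
|---|---|---|
| 85% / 80% | 0.05 × d = 0.010 to 0.025 SD | 4% to 10% |
| 85% / 75% | 0.10 × d = 0.02 to 0.05 SD | 8% to 20% |
| 75% / 75% | 0 | 0 |
| 75% / 85% | −0.02 to −0.05 SD | 8% to 20%, overstating |

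Equal response does not remove the problem if d differs. At 80% in both arms with dC = 0.5 and dT = 0.3, the bias is 0.20 × (0.5 − 0.3) = 0.04 SD.

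**Second model.** Suppose a mother responds when a standard normal transience score falls below the cut-off c that gives response rate p, and the score has correlation ρ with the outcome. The arm mean among responders then shifts by −ρ × φ(c)/p.
- φ(c)/p is 0.274 at p = 0.85 and 0.424 at p = 0.75.
- For 85% / 75%, the bias is about ρ × 0.149: 0.030, 0.045 and 0.075 SD for ρ = 0.2, 0.3 and 0.5. A nominal two-sided 5% test then has type I error of 5.7%, 6.5% and 9.2%.
- For 90% / 70%, the bias is 0.060, 0.091 and 0.151 SD, with type I error of 7.7%, 11.1% and 22.4%.
- With 80% in both arms and a constant effect, the bias is 0. If the effect changes by 0.1 to 0.2 SD per SD of transience, the effect among responders differs from that in all assigned by 0.035 to 0.070 SD.

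**Scale.** At 85% / 75% there are 136 and 120 responders, and the standard error is √(1/136 + 1/120) = 0.125 SD. A bias of 0.02 to 0.05 SD is 16% to 40% of that. At two-sided 5% and 80% power, the smallest detectable difference is 2.8016 × √(2/160) = 0.313 SD with no loss, and 2.8016 × √(2/120) = 0.362 SD at 75% response.

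**The case against.** The strongest reply is that the plan is silent, not wrong. It does not restrict the comparison to responders or rule out imputation or weighting. A reader might infer that it prescribes a responder-only analysis; it does not, although that is the default when nothing else is specified.

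A reader might also infer that the plan expects transience to determine who is reached, or ties non-response to hardship. It says only that some mothers will be harder to reach because the sample is transient. The hardship link is an inference, drawn partly from housing hardship being an outcome.

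The case for response differing by arm can also be challenged. Columbia staff trace mothers from the same sources in both arms: the baseline interview, replies to the mailing and the 10-month interview. Nothing says RtG passes on updated contact details. Controls receive a gift tote and a Columbia call inviting them to stay in the study, which could help or harm their retention. Differential willingness remains possible but is undocumented.

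It is tempting to say that the error must grow from 10 to 42 months. It need not, because with a common d the bias depends on rT − rC and not on total loss.

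These replies limit the claim. They do not supply an analysis set or a missing-data method, and the retention measures do not say how remaining losses will be handled.

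**Conclusion.** The gap is real and worth closing before the arms are compared, but it is not evidence that the results will be biased. The documents support this much: the question is about assignment, outcomes exist only for responders, uneven response is foreseen, and nothing specifies how the two are to be reconciled. Size and direction cannot be determined. Under assumed response of 85% against 75% and d of 0.2 to 0.5 SD in both arms, the bias is 0.02 to 0.05 SD towards the null. That is modest beside a standard error of 0.125 SD. Larger gaps between arms or a stronger link to the outcome would make it matter more.

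A reader might also infer that every input for a better analysis is already held. The documents do not show this. Demographics (including income), depression and stress are expressly placed at baseline. Hardship is not assigned to a wave, and some hardship measures are still to be developed. A 10-attempt trigger does not show that attempt counts are stored as data.

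**What to change.** Amend the closing paragraph of Statistical Procedures as follows.

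1. Analyse mothers by assigned arm and define the analysis set. Randomisation takes place when the baseline visit is scheduled, before signed consent (Informed Consent Process). Mothers lost before baseline should therefore be counted by arm, and the plan should say whether they are within the 160 per arm.
2. For depression and general stress (CES-D and PSS), stated to use the same measures at baseline and follow-up, fit one longitudinal mixed model over baseline, 10, 25 and 42 months with arm-by-wave terms. Add hardship if the same measure is confirmed at baseline. The Parenting Stress Index is cut to one subscale at 10 months, so check comparability before including it.
3. For outcomes measured once, including the in-person assessments offered only to 42-month completers, use multiple imputation or inverse-probability-of-response weights. Build them from arm, baseline demographics, income, depression, stress and earlier-wave outcomes.
4. Report response by arm at each wave. Settle who is approached at 42 months, because section 2 refers to consent at 25 months and the consent description to agreement at baseline.
5. Add a sensitivity analysis for data not missing at random, such as a delta shift varied by arm. If attempt counts are stored, late responders can inform the shift for unreached mothers. They cannot do so for refusers, who are not offered the extra $15.

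The cost is plan wording and modest programming, with no new data collection. The main estimates would rest on a stated missing-at-random assumption, and weights may slightly widen intervals. The baseline measurements should add some precision for depression and stress.
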